Early administration of basal insulin has seldom been studied in DKA management. In 2012, Hsia et al (4) conducted a prospective randomized controlled trial involving 61 hospitalized adults with known diabetes and presented by hyperglycemia who were randomized to receive treatment with IV insulin infusion (IVII) with or without glargine (0.25 Unit/kg). The primary outcome of rebound hyperglycemia was reduced with early administration of glargine (33.3% vs 93.5%, $P < 0.001$) without increasing the risk of hypoglycemia (none in the intervention group vs three cases in the control group). Accordingly, in 2013, the Joint British Diabetes Societies updated their guideline on DKA management in adults to advise early administration of home basal insulin dose (5). After that, two randomized controlled trials were published in 2015, both with a sample size of 40 patients, investigated initiating Insulin Glargine within 2-3 hrs from IVII initiation compared to IVII alone, using a dose of 0.3 unit/kg (6) and 0.4 unit/kg (7). Although both the studies did not demonstrate statistical significance in the primary and secondary outcomes, it could be argued they were clinically significant. For examples, time to AG closure 13 +/- 6 vs 16 +/- 6 hours, IVII dosage 84 ±45 U vs 116 ± 91 U, rebound hyperglycemia for 24 hours after DKA resolution 35% vs 51%, hospital LOS 5.1 vs 5.9 days (intervention and control groups respectively) (7) and no difference in hypoglycemia events between both groups in both studies.

The limitations in the previous studies such as being underpowered, flaws in reporting data, and lacking a unified management protocol make it difficult to state a definitive evidence-based recommendation for using basal insulin early in DKA in adults. For that reason, we propose prospective, open-label, intervention cohort study to test our hypothesis that an insulin glargine dose of 0.4 Units/kg early administered (within four hours) of IVII initiation in DKA management in adult would be effective and safe in shortening the time to anion gap closure comparing to the standard practice.

II. STUDY OBJECTIVE(S): INCLUDING SPECIFIC AIMS AND/OR HYPOTHESES

Specific Aim 1: Test the hypothesis that early Glargine 0.4 unit/kg administration within 4 hours from IV insulin initiation will provide faster anion gap closure in Diabetic Ketoacidosis management in MICU, at least 20% than late administration.

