Specific Aim 2: Determine the safety of insulin glargine 0.4 unit/kg early administration within four hours from IV Insulin infusion initiation.

III. METHODS

A. Study Design and Methodology:

This will be a prospective, open-label, intervention cohort study including all consecutive adult patients with Diabetes Ketoacidosis (DKA) getting admitted to Fairview Hospital-Medical Intensive Care Unit (FV-MICU). Screening of patient eligibility and informed consent will be done by the MICU admitting physician once the patient gets admitted to MICU. Participants will be given an overview of the study, including study procedures, and potential risks. Participants will be given adequate time to review the consent form and have opportunities to ask questions. After the informed consent process has been completed and a consent form has been signed, a copy of the consent will be provided to the participant and another copy will be secured in the Principle Investigator office in a locked cabinet. Enrolled participants in the intervention group will receive an Insulin Glargine 0.4 Unit/kg within 4 hours from initiating the IV Insulin Infusion, as per the Cleveland Clinic DKA protocol. The remaining of the management will be following the CC DKA protocol including continuing IVII till Anion Gap Closure ($AG \leq 12$), Basal Metabolic Panel Q 2 hrs, and replacing electrolytes as indicated. After closing the anion gap, the decision for giving more Basal Insulin doses will be left to the treating physician's discretion. For patient safety, Point Of Care (POC) blood glucose will be checked hourly before IVII discontinuation. After IVII discontinuation, the BG will be checked with meals, bedtime and 2 am if the patient maintain good oral intake, if not, the BG will be checked q 4 hrs. Target BG 150 – 200 mg/dl during the DKA management and 140 – 180 mg/dl after DKA resolution as per American Diabetes Association recommendations. In case of any hypoglycemia event, this goal will be achieved by using Dextrose containing fluid or carbohydrate enriched oral intake which will be left to the treating physician discretion depending on patient awareness and severity of hypoglycemia. Also, the pre meals and correctional insulin doses after AG closure will be left to the treating physician's discretion. After AG closure the pre meals and correctional insulin doses will be left to the treating physician's discretion. In case of not closing the AG after 24 hours from the initial Glargine dose, the decision for further Glargine doses will be left to the treating physician's discretion.

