
The investigator team will be notified by the MICU attending after each participant enrollment, so one of the team members will present to MICU to collect the data prospectively in a standardized Data Collecting Sheet (DCS) by using REDCap and all protected health information (PHI) will be de-identified. As regards the control group, an E-research request will be submitted to provide a list by

all the consecutive adult patients admitted to FV-MICU with a diagnosis of DKA in the period between January 1st 2019 till the date of IRB approval. Prespecified sample size and matched in basal patient characteristics and DKA severity will be selected as the control group. Data will be collected retrospectively for the control group and will be recorded directly into the DCS in RedCap. Clinical outcomes will be compared between the intervention and control groups. The primary outcome includes time to anion gap closure ($AG \leq 12$). Secondary outcomes include hospital Length Of Stay (LOS), ICU LOS, total IVII dose, the incidence of transitional failure (defined recurrence of DKA after initial IVII discontinuation within 24 hours and requiring reinitiating the IVII), the incidence of hyperglycemia (> 180 mg/dL) and hypoglycemia (defined as ≤ 70 mg/dL, <54 , <40) during 24 hours from Insulin Glargine administration.

B. Definition of main exposures and outcomes:

Diagnosis of DKA will be made by ICD-10-CM code E10.10, E11.10, or meeting the ADA definition; $BG \geq 250$ mg/dl, $AG > 12$, and positive Ketones in serum or urine

DKA classification as the following table from ADA:

	Mild (plasma glucose >250 mg/dl)	Moderate (plasma glucose >250 mg/dl)	Severe (plasma glucose >250 mg/dl)
Arterial pH	7.25–7.30	7.00 to <7.24	<7.00
Serum bicarbonate (mEq/l)	15–18	10 to <15	<10

For the hyperglycemia analysis, patients will be compared in the following categories according to their mean or median (depending on the normality of the data distribution) blood glucose throughout the hospital stay:

- Mean/median BG <80 mg/dL
- Mean/median BG 81-100 mg/dL
- Mean/median BG 101-140 mg/dL
- Mean/median BG 141-180 mg/dL
- Mean/median BG > 180 mg/dL'
- Mean/median BG > 240 mg/dL

Hypoglycemia will be defined by three categories:

- any glucose level below 70 mg/dL
- any glucose level less than 54 mg/dL
- any glucose level less than 40 mg/dL

For Time of Anion Gap Closure (TAGC) will use the ADA definition: $AG \leq 12$ mEq/L

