Transitional failure will be defined as the recurrence of DKA ($BG \geq 250$ mg/dl, $AG > 12$, and positive Ketones in serum or urine) after initial IVII discontinuation within 24 hours and requiring reinitiating the IVII.

C. Study Population

Intervention vs Control group

- Intervention group: All consecutive adult patients getting admitted to FV- MICU and meet the inclusion criteria and accepted to receive insulin glargine early as per the protocol. They will receive insulin glargine 0.4 unit/kg within 4 hours from initiating the IV Insulin Infusion, as per the Cleveland Clinic DKA protocol.
- Control group: prespecified and matched sample size, consecutive adults who admitted to FV-MICU with a diagnosis of DKA in the period between January 1st 2019 till the IRB approval date and didn't receive basal insulin before AG closure.

Inclusion criteria:

- Age \geq 18 years old
- Meet DKA definition as above
- Having the capacity to sign Informed consent

Exclusion Criteria

- IV insulin infusion initiated more than 4 hours.
- Persistent hypotension (SBP<80 mmHg despite receiving 1000cc normal saline).
- Require Vasopressor
- Acute Coronary Syndrome
- Pregnant
- End-stage renal disease
- Unwilling to consent to participate in the trial
- Currently under police custody
- Transferred from another hospital
- Require emergent surgery
- Alcoholic Ketoacidosis

Study Variables:

General Informations:

- Patient name
- MRN
- Age
- Sex (Male, Female, Others)
- Race (White, Black, Asian, Other)
- Ethnicity (Hispanic vs. Non-Hispanic)
- Weight on admission (kg)
- BMI (Kg/m²)
- Height (cm)
- Date of Hospital admission
- Date of ICU admission

- Date of DKA diagnosis (MM/DD/YY)
- Precipitating cause of DKA
 - Noncompliance
 - New-onset
 - Infection
 - Cerebrovascular accident
 - alcohol abuse
 - pancreatitis
 - Drugs
 - Others

Past Medical history

- Type of diabetes:
 - Type 1 DM
 - Type 2 DM
 - Cystic fibrosis-related diabetes
 - Steroid-induced diabetes
 - Other or no clear diagnosis
- Known diagnosis of other major medical comorbidities (CAD, CHF, HTN, COPD, asthma, liver disease, CKD, cancer, other)
- On Renal Replacement Therapy (Y/N)
- Using Basal insulin at home (Yes/No/ unknown)
- If previous point answer is yes check the corresponding insulin type and write the dose: (Glargine, Detemir, Degludec, NPH, Continuous Insulin Pump) (dose: IU)
- Home total basal insulin dose (units)

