- Non-insulin antihyperglycemics taken at home prior to admission, including the type
 - Sulfonylureas
 - Thiazolidinediones
 - Dipeptidyl peptidase-4 (DPP-4) inhibitors
 - Biguanides
 - Glucagon like peptide-1 (GLP-1) analogues
 - Sodium-glucose transport protein 2 (SGLT2) inhibitors
 - Meglitinides
 - Alpha glucosidase inhibitors
 - Amylin analogues
- History of immunosuppression (history of cancer, HIV or auto-immune disease or organ transplant, chronic steroid)

Initial Laboratory values:

- Anion gap (mEq/L)
- Bicarbonate (mEq/L)
- Glucose (mg/dL)
- Beta-Hydroxybutyrate (mmol/L)
- Ketones in the urine (Y/N/Unknown)
- HbA1c %
- Lactate (mmol/L)

Intervention and outcomes:

- IV insulin infusion starting time
- Insulin glargine administration time
- Anion Gap closure time
- IV insulin discontinuation time
- Number of hours of IVII
- Total IV insulin infusion has been given
- Total IV insulin/weight
- Total IV fluid during DKA management
- Date of discharge from ICU
- Date of discharge from hospital
- Hospital Length Of Stay (days)
- ICU LOS (hours)
- Transitional failure (recurrence of DKA)?

Hypoglycemia Events

- Hypoglycemia event within 24 hrs from glargine
- Time of the hypoglycemia
- How many hours after the glargine administration?
- Severity
- How it has been treated

Hyperglycemia Events

- Hyperglycemia Event after IVII discontinuation by 24 hours (Y/N)
- time of the hyperglycemia event
- Severity of hyperglycemia
- How many hours after IVII discontinuation

D. Outcomes

Primary outcome: Time to anion gap closure (hours).

Secondary outcomes:

- Hospital Length of stay (days)
- ICU length of stay (hours)
- Total IV insulin infusion dose (International unit)
- Incidence of transitional failure (percentage).
- Incidence of hyperglycemia (> 180 mg/dL) during 24 hours from Insulin Glargine administration (percentage).
- Incidence of hypoglycemia (defined as ≤ 70 mg/dL, <54, <40) during 24 hours from Insulin Glargine administration (percentage).

IV. DATA COLLECTION

For the control group, the data will be collected retrospectively and recorded in standardized DCS in RedCap. For the intervention group, the data will be collected prospectively by the investigator team members and observations will be recorded in standardized DCS in RedCap. All protected health information (PHI) will be de-identified for both intervention and control group by using de-identification function in REDCap.

V. DATA ANALYSIS

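### Transitional failure counts only at glucose of 250 mg/dL or more, a condition early glargine is expected to change, so recorded rates do not cleanly measure failed transitions

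*Combined protocol and SAP*

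**What the plan says.** Section III.B gives the operative definition: "Transitional failure will be defined as the recurrence of DKA ($BG \geq 250$ mg/dl, $AG > 12$, and", continuing "positive Ketones in serum or urine) after initial IVII discontinuation within 24 hours and requiring reinitiating the IVII". All four elements (glucose, AG, ketones, infusion restart) must therefore be present.

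Section III.A words the same outcome without a glucose, AG or ketone threshold: "defined recurrence of DKA after initial IVII discontinuation within 24 hours and requiring reinitiating the IVII". At entry the plan is looser than at recurrence: "Diagnosis of DKA will be made by ICD-10-CM code E10.10, E11.10, or meeting the ADA definition", so a coded patient need not have met the glucose criterion.

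Section III.D lists the outcome as secondary: "Incidence of transitional failure (percentage"). The Study Variables list gives it one yes/no-type item. It has no field for the restart time or for glucose, AG or ketones at recurrence.

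On monitoring, Section III.A states: "After IVII discontinuation, the BG will be checked with meals, bedtime and 2 am if the patient maintain good oral intake", or every 4 hours otherwise. No AG or ketone test is stated for the period after the infusion stops. Control data are read retrospectively and intervention data are collected prospectively.

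On the drug's effect on glucose, the background reports of one trial that "The primary outcome of rebound hyperglycemia was reduced with early administration of glargine (33.3% vs 93.5" percent), and of another "rebound hyperglycemia for 24 hours after DKA resolution 35% vs 51" percent, the latter not statistically significant.

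**The concern.** The outcome is meant to show whether ketoacidosis returns after the infusion is stopped. One of its required components, glucose of at least 250 mg/dL, is something the study drug is expected to lower. If early glargine shifts glucose downward in patients whose ketoacidosis recurs, some of those recurrences drop out of the count even though the gap reopened, ketones were present and the infusion was restarted. The recorded rate can then fall with no change in the true rate. No other outcome or sensitivity analysis in the plan counts such a patient, and the listed data fields would not allow re-scoring without going back to the charts.

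**Working it through.** **The plan's own figure.** No rate or power is given for transitional failure; the only sample size is for the primary outcome (Section V). With control mean 15.6 h, SD 6 h, a 20% difference, one-sided alpha 0.025 and power 90%:

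- difference = 0.20 × 15.6 = 3.12 h
- n per group = 2 × (1.960 + 1.282)² × 6² / 3.12² = 77.7, so 78 per group and 156 in total. The t-test version gives 79 per group and 158 in total.

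The stated 160 is reproduced. It serves here only to supply 80 per group. A 1:1 split is an assumption, as the plan does not state one.

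**Effect of the glucose condition.** Let r be the true rate of recurrence (AG above 12, ketones, infusion restarted), equal in both groups. Let s be the share of recurrences with glucose of at least 250. The recorded rate is r × s, so the recorded rate ratio is s(glargine) / s(control), whatever r is.

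The documents give neither r nor s. Assumed: s(control) = 0.90 and s(glargine) = 0.90, 0.70, 0.50 or 0.30. The ratios are 1.00, 0.78, 0.56 and 0.33, against a true ratio of 1.

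The chance of a one-sided Fisher exact p < 0.025 favouring glargine is the sum of the products of the two binomial probabilities (80 per group) over all tables that reach that level:

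| True rate r | Recorded control | Recorded glargine at s = 0.90 / 0.70 / 0.50 / 0.30 | Chance of p < 0.025 |
|---|---|---|---|
| 5% | 4.5% | 4.5 / 3.5 / 2.5 / 1.5% | 0.7 / 1.4 / 2.8 / 5.6% |
| 10% | 9% | 9 / 7 / 5 / 3% | 1.3 / 3.7 / 9.6 / 23.2% |
| 20% | 18% | 18 / 14 / 10 / 6% | 1.6 / 6.9 / 23.8 / 58.5% |

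Counting recurrences regardless of glucose sets s to 1 in both groups and returns the ratio to 1.

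**Effect of the ketone condition.** Let t be the share of such restarts with a ketone result on record, and suppose that untested restarts are scored as no failure (the plan does not say) and that testing does not depend on glucose. The recorded ratio becomes s(glargine) t(glargine) / [s(control) t(control)]. It equals 1 when t(control) / t(glargine) = s(glargine) / s(control). In the mildest case above, for instance, it equals 1 if controls are tested 0.78 times as often. Less testing in retrospective controls would thus offset the glucose effect and could reverse it.

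**The case against.** The strongest defence is that Section III.B simply reapplies the protocol's own ADA criteria to recurrence, which is a defensible choice for specificity. That explains the choice, but it does not remove the dependence on a component the drug acts on.

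A reader might infer that the definition favours glargine by construction. The documents do not support that:

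- They do not show that glargine lowers glucose in recurrent cases without also suppressing ketosis; their hypothesis is faster gap closure.
- Section VIII describes glargine after gap closure as common practice, so controls may also have basal insulin on board during the 24-hour window.
- Suppose the infusion stops at closure, at about 0.8 × 15.6 = 12.5 h. With the early dose given at 0 to 4 h, the window then opens 8.5 to 12.5 h and closes 32.5 to 36.5 h after that dose. Later basal doses are discretionary, so the glucose difference could shrink or reverse.
- Missing ketone tests in controls would act in the opposite direction.

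A reader might also size the bias from the background's rebound figures, for example 10% × 33.3% = 3.3% against 10% × 93.5% = 9.4%. That is not valid. Those are rebound hyperglycemia rates among trial patients, not shares of ketoacidosis recurrences reaching 250. The background states no threshold for rebound, and the protocol's own hyperglycemia cut-off is 180. The first trial enrolled adults presenting with hyperglycemia and used 0.25 Unit/kg; the 35% vs 51% result was not significant.

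These objections stand against any claim of size or direction. They do not answer the basic point that a ketotic recurrence with infusion restart below 250 goes uncounted.

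**Conclusion.** The point holds as a weakness of definition, not as a demonstrated bias. A difference in recorded transitional failure, in either direction, could reflect glucose level or ketone testing rather than failed transitions. The 3.7% to 23.2% range (true rate 10%) and the 1.4% to 5.6% range (true rate 5%) rest wholly on assumed recurrence rates, assumed shares reaching 250, a 1:1 split and Fisher's exact test. They show what could happen, not what is expected. Severity is minor: this is an unpowered secondary outcome, and time to gap closure and N = 160 are untouched.

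**What to change.** 1. In Sections III.A and III.B, use one definition: infusion restarted within 24 hours of first discontinuation with AG above 12 and positive ketones, regardless of glucose. Report the full glucose, AG and ketone definition alongside it.
2. Add to the data sheet, for both groups, the restart time and the AG, glucose and ketone result at restart, with an explicit code for not tested.
3. Report restarts with AG above 12 but no ketone test as a sensitivity analysis.

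Ketones should stay in the main definition. Dropping them as well would count restarts with a raised gap from other causes and would lean more heavily on an open-label restart decision.

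The cost is a few fields read from the chart and a slightly broader event. No extra tests are implied. Recurrences for which no AG or ketones were measured will stay hidden, and the report should say so.

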The sample size calculation considered the average time of AG closure in the last 3 months in FV-MICU was 15.6 ± 2.5 hours (CI 95%) and SD of 6 hours. Using one-sided α of 0.025 and an β of 0.10, an expected 20% difference between the two groups, a sample size of 160 totally of the participant will be adequate.

Categorical variables will be described as frequency rates and percentages, and continuous variables will be described using mean, median, and interquartile range (IQR). Proportions for categorical variables will be compared by Chi-squared test of Fisher's exact test. Means for continuous variables will be compared by Student's t-test if normally distributed and Mann-Whitney test if not normally distributed. All statistical analyses will be performed with a one-sided p-value < 0.025 to determine statistical significance. All statistical analyses will be completed by study investigators using Statistical Analysis Software (SAS).

VI. DATA AND SAFETY MONITORING PLAN (if applicable)

All data will be stored in a secured REDcap database. No PHI will be saved on non-HIPAA protected devices. All protected health information (PHI) will be de-identified by using RedCap.

To ensure patient safety, CCF Hypoglycemia protocol is getting followed in all patients receiving insulin including our enrolled participants. Before IV insulin discontinuation, the blood glucose level is getting checked hourly as per protocol. Once the AG is closed and insulin infusion is discontinued, the patient who is maintaining oral intake, blood glucose will be checked with meals, bedtime, and 2 am. If the patient having poor oral intake, blood glucose will be checked q 4 hours. Different treatment options for any hypoglycemic events are available in the protocol depending on the severity of the hypoglycemia event and patient awareness, ranging from oral carbohydrate supplement to IV fluid containing dextrose.

VII. STUDY LIMITATIONS

- Retrospective EPIC data review for the control group. Single-center.

VIII. ETHICAL CONSIDERATIONS

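### The listed variables include no laboratory measure of kidney function, so renal impairment at presentation could not be matched, adjusted for or shown at baseline in this non-randomized comparison

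*Combined protocol and SAP*

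**What the plan says.** All references are to the combined protocol and SAP.

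- **History items** (III.C, Study Variables, Past Medical history): "Known diagnosis of other major medical comorbidities (CAD, CHF, HTN, COPD, asthma, liver disease, CKD, cancer, other" and, on the next line, "On Renal Replacement Therapy (Y/N".
- **Exclusion** (III.C, Exclusion Criteria): "End-stage renal disease". No criterion concerns lesser or acute renal impairment.
- **Initial Laboratory values** (III.C): the list opens with "Anion gap (mEq/L" and closes with "Lactate (mmol/L". Between them are bicarbonate, glucose, beta-hydroxybutyrate, urine ketones and HbA1c. Creatinine, BUN and eGFR are absent, and no acute kidney injury variable appears elsewhere.
- **Routine monitoring** (III.A): "Basal Metabolic Panel Q 2 hrs, and replacing electrolytes as indicated". The contents of the panel are not given.
- **Control group** (III.A): "Prespecified sample size and matched in basal patient characteristics and DKA severity will be selected as the control group". Apart from DKA severity, no matching variable is named, and no matching method is given. Section VII lists as a limitation "Retrospective EPIC data review for the control group. Single-center".
- **Analysis** (V): continuous outcomes are compared by t-test or Mann-Whitney, and proportions by chi-squared or Fisher's exact test. There is no covariate model.

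**The concern.** Neither a known CKD diagnosis nor a renal replacement flag measures renal function on arrival. A patient with no renal history but impaired function at presentation looks the same in the listed data as a patient with normal function.

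The gap touches both aims. The primary outcome is time until the anion gap is 12 or less, and retained acids in renal impairment can hold the gap open after ketosis has cleared. Aim 2 is safety, and reduced renal function can prolong insulin action and so bear on hypoglycemia. The plan already records beta-hydroxybutyrate and lactate, two contributors to the gap, but not this one.

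In a randomized trial this would be a minor omission. Here the treated patients are prospective and consenting, the controls are selected from charts, and the tests are unadjusted. A prognostic factor that is not recorded cannot be balanced by design, corrected in analysis or displayed in a baseline table.

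**Working it through.** **1. The plan's own figure.** Section V gives a mean of 15.6 h, SD 6 h, a 20% difference, one-sided α = 0.025 and β = 0.10. Allocation is not stated; I assume 1:1.

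- Target difference: 0.20 × 15.6 = 3.12 h.
- n per arm = 2 × (1.960 + 1.282)² × 6² / 3.12² = 77.7, rounded up to 78, or 156 in total. The noncentral t calculation gives 79 per arm, 158 in total.

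The stated 160 is reproduced. This point does not depend on it, but 80 per arm fixes the standard error used below.

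**2. Standard error.** SE = 6 × √(2/80) = 0.949 h. Power for 3.12 h is Φ(3.12/0.949 − 1.960) = 90.8%.

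**3. Bias from an unrecorded factor.** Bias in the mean difference = (difference between groups in the proportion with renal impairment) × (extra hours to closure that impairment causes). The documents supply neither input. The ranges here are assumptions: 10 to 30 percentage points, and 2 to 6 h. No attenuation from severity matching is assumed.

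**4. Effect on the one-sided type I error if the bias favours glargine:** 1 − Φ(1.960 − bias/0.949).

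| Imbalance | Extra hours | Bias (h) | Share of 3.12 h | Type I error |
|---|---|---|---|---|
| 10 points | 2 | 0.2 | 6% | 0.040 |
| 10 points | 4 | 0.4 | 13% | 0.062 |
| 10 points | 6 | 0.6 | 19% | 0.092 |
| 20 points | 2 | 0.4 | 13% | 0.062 |
| 20 points | 4 | 0.8 | 26% | 0.132 |
| 20 points | 6 | 1.2 | 38% | 0.244 |
| 30 points | 2 | 0.6 | 19% | 0.092 |
| 30 points | 4 | 1.2 | 38% | 0.244 |
| 30 points | 6 | 1.8 | 58% | 0.475 |

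**5. If the bias runs the other way,** the cost is power: Φ((3.12 − bias)/0.949 − 1.960). A bias of 0.2 h gives Φ(1.118) = 87%, and 1.8 h gives Φ(−0.569) = 28%.

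**6. Hypoglycemia.** The documents give no planning event rate for this trial, so I have not attempted a comparable calculation.

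**The case against.** The strongest reply is that this is one instance of a wider gap. The plan has no adjustment model and no named matching set, so recording creatinine alone would leave the planned t-test or Mann-Whitney unchanged. That stands, and the fix must therefore include the analysis.

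Second, baseline anion gap, bicarbonate and lactate are collected and DKA severity is matched. These are partial proxies for acid load and illness severity, so part of a renal effect on closure may already be captured. That also stands, and it means the table shows the effect before any such attenuation. The proxies do not address prolonged insulin action.

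Third, a single creatinine at infusion start cannot separate acute from chronic impairment without an earlier value. True, but renal function at presentation is what the comparison needs, whatever its cause.

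A reader might draw three stronger conclusions that the documents do not support:

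- *That an imbalance could never be detected or corrected.* Control data come from chart review, and the record number is a listed variable. If creatinine was measured, it should be retrievable for both groups. The Data Collecting Sheet is named as an appendix but is not shown, and it may already hold the field. The supportable statement is that creatinine is not listed.
- *That the bias favours glargine because treated patients must have capacity to consent.* This is plausible, but nothing in the plan links capacity to renal function. The exclusions for persistent hypotension, vasopressors and end-stage renal disease, if applied to controls as well, would remove the most unstable patients from both groups.
- *That the panel drawn every 2 hours is stated to contain creatinine.* That is its usual content, but the plan does not say so.

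**Conclusion.** The point holds as a gap in the listed variables and the planned analysis. Kidney function enters only through two history items and one exclusion. Followed as written, the plan would leave a plausible prognostic factor for both gap closure and hypoglycemia unmatched, unadjusted and unreported.

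Its size is illustrative only. Given 1:1 allocation, 80 per arm, SD 6 h, the assumed ranges and no attenuation, the bias is 0.2 to 1.8 h, and the type I error is 0.04 to 0.475 if glargine is favoured. The width of that range reflects the assumed inputs, so no single value from it should be cited as this trial's false-positive rate. The point does not show that the result will be biased, nor in which direction. It is a low-severity design improvement, worth making because it is cheap.

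**What to change.** 1. Add creatinine, with eGFR, at the start of the IV insulin infusion to the Initial Laboratory values for both groups. Take it from the routine metabolic panel (assumed to include creatinine) or from the chart. If the Data Collecting Sheet already has the field, bring the Study Variables list into line with it.
2. Name the matching variables in III.A and include renal function among them.
3. In section V, replace the unadjusted primary test with a regression comparison of time to anion gap closure, adjusted for baseline anion gap or DKA severity and for renal function.
4. Show renal function by group in the baseline table. Any breakdown of hypoglycemia by eGFR should be descriptive only, since 160 patients will not support a subgroup test.

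The cost is one extra data field per patient and a simple regression model. If the panel includes creatinine, no new blood draw is needed, and clinical care does not change. Settling this before control data are collected avoids a second pass through the charts.

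### Length of stay is compared with no vital status or discharge disposition in the protocol's variable list, so stays cut short count as favourable and deaths are not compared under the safety aim

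*Combined protocol and SAP*

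**What the plan says.** Section III.D lists six secondary outcomes. Two of them are hospital length of stay in days and ICU length of stay in hours.

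The Study Variables list in III.C, under Intervention and outcomes, marks the end of each stay with "Date of discharge from ICU" and "Date of discharge from hospital", and then lists the two derived lengths of stay. It has no item for vital status, date of death, discharge destination, departure against advice or transfer out. Transfer in from another hospital is an exclusion, but transfer out is not mentioned.

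Section V treats length of stay like any other continuous variable: "Means for continuous variables will be compared by Student's t-test if normally distributed and Mann-Whitney test if not normally distributed". It gives no rule for stays that end in death or early departure.

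Specific Aim 2 is worded generally: "Determine the safety of insulin glargine 0.4 unit/kg early administration within four hours from IV Insulin infusion initiation". The adverse outcomes in III.D are hypoglycemia, hyperglycemia and transitional failure. Sections VI and VIII discuss patient safety in terms of glucose monitoring and the handling of hypoglycemia. Section VIII also commits the investigator to sending safety updates to the IRB.

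**The concern.** A short stay is the favourable direction. A patient who dies or leaves on day 1 has a one-day stay on the recorded dates, and the planned test cannot tell that patient from one who recovered quickly. An excess of such exits in the glargine group would look like benefit. An excess among controls would hide benefit.

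Equal exit rates cannot be taken for granted, because the groups are assembled differently. Intervention patients are enrolled prospectively, must have capacity and consent, and accept early glargine. Controls are picked from charts and matched on baseline characteristics and DKA severity, and historical patients cannot have met the consent criterion in the same way. Departure against advice is foreseeable, since noncompliance and alcohol abuse are among the listed precipitating causes.

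The second consequence concerns Aim 2. A conclusion about safety in patients admitted to a medical ICU would normally be accompanied by the number of deaths in each group. Nothing in the listed variables, outcomes or analyses provides for that.

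**Working it through.** **The plan's own figure.** Section V gives a mean of 15.6 h, an SD of 6 h, a 20% difference, one-sided α = 0.025 and β = 0.10. The allocation ratio is not stated; 1:1 is assumed.

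- δ = 0.20 × 15.6 = 3.12 h
- n per group = 2 × (1.960 + 1.282)² × 6² / 3.12² = 77.7, rounded up to 78, so 156 in total

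This agrees with the stated 160 (80 per group). The figure concerns time to anion gap closure and does not depend on the present point. No figure is given for length of stay or deaths.

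**Effect of early exits on mean length of stay.** The documents give no rate of death or early departure, so the rows below are assumptions and not estimates. For scale, the background cites hospital stays of 5.1 days (glargine) and 5.9 days (control) from the 0.4 unit/kg trial, a difference of 0.8 day. If k is the net excess of early exits in one group of 80, and each exit at day t replaces a 5.9-day stay, then

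shift in the mean difference = k × (5.9 − t) / 80

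| Net excess k | Exit at day 1 | Share of 0.8 day | Exit at day 2 | Share of 0.8 day |
|---|---|---|---|---|
| 1 | 0.06 | 8% | 0.05 | 6% |
| 2 | 0.12 | 15% | 0.10 | 12% |
| 4 | 0.25 | 31% | 0.20 | 24% |
| 8 | 0.49 | 61% | 0.39 | 49% |

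For example, with k = 1 and t = 1, (5.9 − 1)/80 = 0.061 day, and 0.061/0.8 = 8%. Because k is a net count, four exits in one group and two in the other give the k = 2 row.

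These shifts apply to means. If length of stay is not normally distributed, section V moves to the Mann-Whitney test. Short stays still receive favourable ranks there, but the effect is not the one in the table.

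**Deaths.** The chance of at least one death among 160 patients is 1 − (1 − p)^160. For assumed risks p of 0.2%, 0.5%, 1%, 2% and 5% this is 27%, 55%, 80%, 96% and about 100%. If no deaths occurred in a group of 80, the exact upper 97.5% limit would be 1 − 0.025^(1/80) = 4.5%. Both the count and the limit require vital status to be recorded.

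**The case against.** - **The data sheet may hold the field.** The Data Collecting Sheet is named as an appendix but its content is not shown, so a reader should not infer that deaths or disposition will go unrecorded. What stands is that the protocol's detailed variable list, its outcomes and its analysis make no use of such a field.
- **Deaths are probably few.** The criteria exclude vasopressor need, persistent hypotension, acute coronary syndrome, emergent surgery and end-stage renal disease, and require capacity to consent. An ICU setting might suggest appreciable mortality, but the documents do not support that. This stands, and it is why early departures may matter more for length of stay. A late death also need not shorten the stay.
- **The larger shifts are not a prediction.** A reader might infer a bias of a quarter or half a day. That requires four or eight exits in one group with none in the other, all at day 1 and all replacing a full 5.9-day stay. Patients who leave early might have had shorter stays anyway.
- **The benchmark is soft.** The background says only that clinical significance could be argued for the cited differences, and reports that they were not statistically significant.
- **Deaths are not invisible.** It would be too strong to say that they can never bear on safety, because the IRB receives safety updates. Those updates are not a comparison with the historical controls. A count at this sample size would also say little about comparative mortality, as the 4.5% limit shows, but it is still the least that a general safety aim should report.

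**Conclusion.** The gap is real and modest. Followed as written, the plan scores a stay ended early by death, departure against advice or transfer as an ordinary short stay, and does not compare deaths by group under Aim 2.

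The size depends on the between-group difference in early exits, which the documents do not allow anyone to estimate. With 80 per group and day-1 exits replacing 5.9-day stays, the shift is about 0.06 day per net excess exit; the eight-exit row, 0.49 day, is an assumed upper range. The direction of any bias is unknown.

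The documents do not support a claim that the length-of-stay result will be materially wrong, or that deaths will go unseen. The primary outcome and the sample size of 160 are untouched. This is a cheap improvement to two secondary outcomes and to the safety report.

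**What to change.** 1. Add discharge disposition (home, facility, against advice, transferred, died) and vital status at ICU and at hospital discharge to the variable list, abstracted from the chart for both groups. If the Data Collecting Sheet already has these items, bring the protocol list into line with it.
2. State in III.D and V that deaths will be reported by group with exact confidence intervals under Aim 2.
3. State in V how stays that do not end in live discharge are handled. One workable rule gives deaths the worst rank in the length-of-stay comparison; analysing time to live discharge is an alternative. Choose one before the data are seen.
4. Repeat the comparison without departures against advice and transfers. Keep this as a sensitivity analysis, because it excludes patients on the basis of something that happened after treatment began.

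The cost is a small amount of extra abstraction and a few sentences of text, and length of stay is no longer summarised as a simple mean. It is best done before abstraction begins, since the records are to be de-identified and going back to the chart later may be harder.
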